7.4 Ferumoxytol Magnetic Resonance Imaging

It is anticipated that the MRI parameters will need to be optimized in patients that are enrolled at the beginning of the study and/or in the Expansion Phase, in order to assess any correlations between FMX-MRI signal and TAMs, pharmacodynamic markers, or tumor response. A detailed FMX-MRI protocol is included in the study imaging manual, but briefly, each patient will be required to undergo their FMX-MRIs on the same scanner to reduce inter-scan variability. Each MRI study will be evaluated for image quality and signal characteristics of tumors and reference tissue on T1-, T2- and T2*- weighted sequences. Once a completed set of images from each patient has been received, the images will be loaded onto the viewing workstation for qualitative review and then sent to a quantitative lab for analysis.

During the Expansion Phase, multiple MR images will be collected on Day 1-Day 2 of the ferumoxytol period, at various time points depending on the scan group to which the patient is assigned. The body areas to be scanned will be determined by the location of the patient's disease; detailed instructions are described in the study imaging manual. All patients will have a baseline image acquired prior to the ferumoxytol infusion, and either a second successive image (baseline repeat; Scan Group 1) or a second image occurring 1-4 h after the end of ferumoxytol administration (Scan Groups 2 and 3). All patients will return on Day 2 for a 24 hour (16-24 h window) FMX-MRI using the same protocol and sequences as on Day 1. Patients enrolled into Scan Groups 1 and 2 will require one additional scan either at 24 h or 2 weeks, for a total of 4 scans. Patients will be assigned in an alternating fashion to Scan Groups 1 and 2 before enrollment into Scan Group 3 begins. See Table 14 below for additional details on scan groups and required time points.

Scan Group	N ^a	Baseline	Baseline (repeat)	1-4 h	24 h (16-24 h)	24 h (repeat)	2 wk (+/- 1 Day) Baseline
1	5	Х	Х		Х		Х
2	5	Х		Х	Х	Х	
3	10	Х		Х	Х		

Table 14: Summary of Expansion Phase MRI Scan Groups (Cohorts 1 and 2)

^a Enrollment into Scan Groups 1 and 2 may be increased at the discretion of the Sponsor, in the event that any of the images are not evaluable, or it is determined that more information is needed from the additional scan time points. In this case, enrollment into Scan Group 3 will be decreased by a corresponding number of patients.

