4 SAMPLE SIZE DETERMINATION

No formal hypothesis testing is performed for this study. Therefore, the Pilot and Expansion Phases are not powered to detect statistical differences on any parameters. Results will be descriptive.

The Pilot Phase will enroll 12 to 20 patients with various indications, while the Expansion Phase will enroll approximately 30 metastatic breast cancer patients across three cohorts.

The Expansion Phase ORR is estimated to be around 29% with a 95% confidence interval (14.6-46.3) [Awada, 2013]. Other studies showed similar response rates ranging from 5-32% [Kümler, 2013]. Hypothesizing a true ORR of 30%, the probability of at least 14 responses of 30 evaluable patients would be 0.04. The probability of at least 13 responses would be 0.084.

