11 EFFICACY ANALYSES

11.1 Primary Efficacy Endpoints:

The efficacy endpoints will be summarized for efficacy evaluable population and PD evaluable population by using descriptive statistics.

Pilot Phase:

- **Feasibility of FMX-MRI on identifying tumor associated macrophages (TAMs):**

FMX-MRI will be conducted on day 1 before and 1-4 h after intravenous ferumoxytol (FMX) administration, then after 24 h and/or 72 h. For the quality scan of FMX-MRI, scanner type (i.e. 1.5T), impact of scan quality on analysis (i.e. adequate for evaluation, suboptimal but completed for evaluation, or inadequate for evaluation), reasons for scan suboptimal/inadequate) and scan location (i.e. Body) will be assessed.

- **Tumor Levels of Irinotecan and SN-38:**

During pilot phase, two biopsies are collected on Day 4 of the ferumoxytol phase and two biopsies are collected three days after the first dose of MM-398. Tumor levels of irinotecan and SN-38 in core biopsy will be measured after MM-398 dosing.

Expansion Phase:

- **Feasibility of Ferumoxytol (FMX) Quantitation in Tumor Lesion**

Feasibility of ferumoxytol (FMX) quantitation in tumor lesion is also assessed through the acquisition of baseline and follow-up images of sufficient quality that enable quantitative analysis to be performed.

Eligible patients should have serial FMX-MRI scans prior to and following FMX infusion as determined by their scan group. After MRI acquisition, the R2* signal is used to calculate FMX levels in plasma, tumor lesions and reference tissue by comparison to a phantom-based standard curve.

- **The Relationship Between Ferumoxytol (FMX) tumor uptake and tumor response to MM-398**

FMX-MRI will be done for various tissues and at different timepoints. Corrected FMX uptake (post-baseline value - baseline value) will be recorded by each time point and tissues. Ferumoxytol uptakes will be associated with change in tumor lesion size.

11.2 Primary Efficacy Analysis:

Pilot Phase

In patients with NSCLC, CRC, TNBC, ER/PR positive breast cancer, pancreatic cancer, ovarian cancer, gastric cancer, GEJ adenocarcinoma or head and neck cancer, who are undergoing therapy with MM-398:

- To evaluate the feasibility of delayed ferumoxytol MRI (FMX-MRI) to identify tumor associated macrophages (TAMs)

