The quality of FMX-MRI scan on impact of evaluation will be summarized descriptively by evaluation time points. For the quality scan of FMX-MRI, number of FMX-MRI scans obtained, number of scans accepted for evaluation, and scan location (i.e. Body) at each time point will be assessed. If there is more than one image data at the same timepoint for a patient, image data are averaged first before summarizing.

- To measure tumor levels of irinotecan and SN-38
Tumor levels of irinotecan and SN-38 during Pilot phase were assessed through tumor tissue biopsy. The data are summarized using descriptive statistics with n, min, max, mean 25th percentiles (Q1), 75th percentiles (Q3) and median per lesion. Tumor levels of irinotecan and SN-38 in core biopsy are reported in Merrimack Pharmaceuticals Synopsis Clinical Study Report MM-398-01-01-02, published on 18-Dec-2014 (Appendix X). No further analysis is required.

Expansion Phase

In patients with locally advanced or metastatic breast cancer:

- To further investigate the feasibility of ferumoxytol (FMX) quantitation in tumor lesions

Feasibility of ferumoxytol (FMX) quantitation in tumor lesion is assessed through the acquisition of baseline and follow-up images of sufficient quality that enable quantitative analysis to be performed. Sufficient quality is assessed by summarizing images that are adequate for evaluation, suboptimal but completed for evaluation, or inadequate for evaluation at each visit.

- To characterize the relationship between ferumoxytol (FMX) tumor uptake and tumor response to MM-398

Ferumoxytol uptakes will be associated with change in tumor lesion size. Corrected FMX results (ug/mL) from target lesion(s) at 24-hour scan is used to measure FMX tumor uptake. For the repeated scans performed at the same timepoint, the FMX tumor uptake will be averaged first before summarizing. For patient with multiple target lesions, average corrected FMX results should be used for analysis. FMX uptake will be classified as 'low tumor uptake' or 'high tumor uptake' using overall median as cutoff. Change in tumor size is used to assess tumor response to MM-398. For patient with multiple target lesions, the best change in tumor size achieved should be used. The relationship between dichotomous FMX tumor uptake classification and tumor response to MM-398 will be assessed using Fisher's exact test.

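### Expansion Phase feasibility needs a usable baseline and follow-up image in the same patient, but SAP 11.2 reports image quality only visit by visit, which bounds the paired proportion and can overstate it

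*SAP*

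**What the plan says.** Quantifying FMX in tumor lesions is one of the two Expansion Phase primary objectives (SAP 2.1; Protocol 3.1). SAP 11.1 and 11.2 say it is "assessed through the acquisition of baseline and follow-up images of sufficient quality that enable quantitative analysis to be performed".

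The quantity to be obtained is a difference: "Corrected FMX uptake (post-baseline value - baseline value) will be recorded by each time point and tissues" (SAP 11.1). For the other Expansion Phase primary objective, SAP 11.2 fixes the timepoint: "Corrected FMX results (ug/mL) from target lesion(s) at 24-hour scan is used to measure FMX tumor uptake".

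The planned feasibility summary is one sentence in SAP 11.2: "Sufficient quality is assessed by summarizing images that are adequate for evaluation, suboptimal but completed for evaluation, or inadequate for evaluation at each visit". The SAP sets no per-patient success definition, no denominator for one, and no rule on whether the middle category counts as success.

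On size and intent, SAP 4 says "the Expansion Phase will enroll approximately 30 metastatic breast cancer patients across three cohorts", and "Therefore, the Pilot and Expansion Phases are not powered to detect statistical differences on any parameters".

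On scheduling, every scan group has a baseline and a 24 h scan (Protocol 7.4, Tables 14 and 15). Some have a larger number of scans: "Patients enrolled into Scan Groups 1 and 2 will require one additional scan either at 24 h or 2 weeks, for a total of 4". Group 1 repeats the baseline and Group 2 repeats the 24 h scan.

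**The concern.** The endpoint joins two conditions, baseline and follow-up. The analysis tabulates each one separately. A corrected 24 h value cannot be formed for a patient who lacks a usable image at either timepoint, yet that patient still adds a usable image to the other visit's row. Two rows can therefore look good while fewer patients have a result, and the table does not show whether that has happened.

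What is at stake is a direct answer to a primary objective. Protocol 2.3 presents multi-institutional feasibility of FMX-MRI as an important aim of the Expansion Phase. Anyone planning a later study would want to know in what share of patients, and of lesions, FMX could be quantified. The planned table answers a different question: how images were graded at each visit.

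**Working it through.** **The plan's own figures.** The documents state no feasibility rate, target or threshold, so there is no feasibility figure to reproduce. The only Expansion Phase sizing figures concern response. With a true ORR of 30% and N = 30, the binomial probability of at least 14 responses is 0.0401 (stated 0.04) and of at least 13 is 0.0845 (stated 0.084). Both reproduce, but neither bears on this point.

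**Inputs.**
- N = 30, from SAP 4 (approximate).
- The pair is baseline and 24 h. The feasibility text says only follow-up; 24 h is taken from the uptake measure in SAP 11.2.
- Usable rates at each visit are not in the documents. They are assumed here, from 80% to 100%.

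**Formula.** Take one result per patient per visit, with b patients usable at baseline and f usable at 24 h. The number usable at both lies between max(0, b + f − N) and min(b, f). If failures at the two visits were independent, the expected number is b × f / N.

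| Baseline b | 24 h f | Fewest with both | If independent | Most with both |
|---|---|---|---|---|
| 24 (80%) | 24 (80%) | 18 (60%) | 19.2 (64%) | 24 (80%) |
| 27 (90%) | 27 (90%) | 24 (80%) | 24.3 (81%) | 27 (90%) |
| 28 (93%) | 28 (93%) | 26 (87%) | 26.1 (87%) | 28 (93%) |
| 29 (97%) | 29 (97%) | 28 (93%) | 28.0 (93%) | 29 (97%) |
| 30 (100%) | 27 (90%) | 27 (90%) | 27 (90%) | 27 (90%) |

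For the second row: 27 + 27 − 30 = 24 and min(27, 27) = 27. The exact 95% CI is 61.4% to 92.3% for 24/30 and 73.5% to 97.9% for 27/30. A table showing 90% at each visit is compatible with either.

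**Effect of repeats.** Planned baseline images are 5×2 + 5 + 10 + 10 = 35, and 24 h images are 5 + 5×2 + 10 + 10 = 35, for 30 patients (Cohort 3 body scans not counted). If the table counts repeats as separate images, the bounds above no longer apply. Assume per-image usable rates of 70% at baseline and 95% at 24 h, independent, with either repeat sufficing:
- Group 1: (1 − 0.3²) × 0.95 = 0.8645
- Group 2: 0.70 × (1 − 0.05²) = 0.69825
- Group 3 and Cohort 3: 0.70 × 0.95 = 0.665
- Overall: (5 × 0.8645 + 5 × 0.69825 + 20 × 0.665) / 30 = 0.704

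The patient rate of 70.4% is then slightly above the 70% in the baseline row, so here that row understates it.

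**The case against.** A reader might infer that the trial's primary feasibility rate is overstated. The documents do not support that. The SAP names no single feasibility rate and sets no threshold; it plans a descriptive table. The direction of any error is not fixed either. The paired rate can equal the lower visit rate, and counting repeats as separate images can make a visit row too low. Protocol 7.4 keeps each patient on one scanner, so failures may well cluster within patients, though the documents do not show this.

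A reader might also infer that one bad image leaves a patient with no corrected value. That is not generally so. Scan Groups 1 and 2 have a repeat at one of the two timepoints. Scan Groups 2 and 3 and Cohort 3 also have a 1-4 h scan, which Protocol 10.6 allows in the uptake analysis.

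The strongest objection is that the paired count can largely be recovered. SAP 11.2 reduces the corrected 24 h result to one value per patient, SAP 7.1 and 14 require n for every continuous summary, and a corrected value needs both timepoints. This stands in part. That n is a partial proxy, but it is not labelled as the feasibility result and carries no CI or lesion count. In the PD evaluable population, which SAP 6 assigns to imaging-related efficacy analyses, it is restricted to patients with 8-week radiology. Imaging failure is then mixed with early dropout.

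The fix also involves choices. Using 24 h alone, and requiring at least one lesion, is narrower than the SAP's general reference to follow-up images.

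**Conclusion.** The point holds in a limited form. SAP 11.2 has no output that measures the paired success its own endpoint describes, and the by-visit percentages can overstate it. At an assumed 27/30 per visit the paired proportion is anywhere from 80% to 90%. At 24/30 it is 60% to 80%; at 29/30 the gap is at most one patient. These sizes rest on assumed adequacy rates, N = 30, one result per patient per visit, and 24 h as the follow-up. They show what the table cannot distinguish and do not predict what will be found.

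Because the study is descriptive and a partial proxy exists, this is a cheap improvement. It does not invalidate the objective.

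**What to change.** In SAP 11.2, Expansion Phase feasibility, add a per-patient result:
- **Definition.** Success is a corrected 24 h FMX value obtained for at least one target lesion; 24 h is the timepoint used for the primary uptake measure.
- **Suboptimal images.** An image graded suboptimal but completed counts as usable if a corrected value was derived from it.
- **Repeats.** Where a timepoint is repeated, one usable image suffices.
- **Reporting.** Give n/N with an exact 95% CI by cohort and overall, and say which population N is. Give target lesions quantified out of target lesions scanned alongside it.
- **Supporting detail.** Keep the by-visit quality grades.

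The cost is SAP wording and one derived flag. Every scan group already has both scans scheduled and Protocol 7.4 already has each MRI study evaluated for image quality, so no new data are needed. The downside is that the stated rate may be less favourable than the visit rows suggest.

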10.6 Efficacy Analysis

Tumor evaluation will be measured according to Response Evaluation Criteria In Solid Tumors (RECIST) version 1.1 (Cohort 1 and 2, and non-CNS disease for Cohort 3) or modified RECIST

as defined in section 7.1.6.1 (CNS disease; Cohort 3 only). Best Overall Response (BOR) is defined as the best response as recorded from the start of MM-398 until disease progression.

Objective Response Rate (ORR) is defined as the proportion of patients with a BOR characterized as either a Complete Response (CR) or Partial Response (PR) relative to the total number of evaluable patients. Exact 95% confidence intervals based on the binomial distribution will be reported.

Clinical benefit rate is defined as the proportion of patients with a BOR characterized as a CR, PR, or Stable Disease (SD) \geq 24 weeks. Proportion of patients relative to the total number of evaluable patients will be reported with exact 95% confidence intervals based on the binomial distribution.

Duration of Response (DR) is defined as the time from first documentation of response (CR or PR whichever occurs first) to the date of disease progression or to death due to any cause, whichever occurs first.

Progression-free survival (PFS) is defined as the time from first dose of MM-398 to the date of radiologic disease progression by RECIST per Investigator or death due to any cause, whichever occurs first. Rules for declaring PFS events versus censors will be described in the SAP.

A waterfall plot will be used to display BOR with maximum percent decrease in target lesion and FMX uptake value at 24 hours.

FMX uptake (ug/mL and/or %ID/kg) will be summarized as a continuous parameter. Absolute and change from baseline will be summarized. The number of target lesions decreasing, staying the same, increasing relative to FMX uptake with various thresholds will be summarized by frequency and percent according to cycle. Box and whisker plots will be displayed for FMX uptake by time point. The relationship between FMX uptake at 1-4 hours and/or 24 hours with tumor response will be evaluated using various parameters and methods. Relationships may be explored as appropriate. Additionally, informal Fisher's exact test will be used to investigate dichotomous FMX cutpoints as related to ORR. Other graphical procedures may be implemented to explore the relationship between FMX and efficacy response.

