11.3.1 Tumor Response-related Variables

- Investigator determined tumor response assessment

Investigator determined tumor assessments will be performed at baseline and at 8-week intervals following initiation of MM-398. Overall tumor response for post-baseline assessments will be classified as Complete Response (CR), Partial Response (PR), Stable Disease (SD), Progressive

Disease (PD), Not Evaluable (NE) or Non-CR/Non-PD (no-target disease only) per RECIST version 1.1 criteria or modified RECIST criteria for cohort 3 CNS disease only.

For each tumor assessment, investigators will evaluate and report on the CRF a classification of overall tumor response and its components (target lesions, non-target lesions, and new lesions). Main analyses of tumor response related variables will be based on the investigator assessment of tumor response.

Derived efficacy evaluations including progression-free survival, best overall response, and objective response rate will be based on investigator determined tumor response data.

- Radiological tumor response assessment

In addition to investigator determined tumor response assessment, tumor that have FMX uptake measurement will also be measured radiologically in central facility. Response classifications will be algorithmically computed from the data on target lesions, non-target lesions and new lesions. The radiological tumor response will be reported separately for associating with ferumoxytol (FMX) uptake.

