11.3.2.5 Duration of Objective Response (DOR)

DOR is defined as the time from first documentation of response (CR or PR whichever occurs first, by investigator assessment) to the date of disease progression or to death due to any cause, whichever occurs first. Duration of response will be computed only for patients who have CR or PR as best overall response. If progression or death does not occur for a patient with response, the patient's duration of response will be censored in accordance with the rules used for PFS analysis. Duration of objective response will be calculated for all patients that experience documented objective response during the study in weeks as follows:

Duration of DOR (Months) = ((Date of Progression/Death/Censoring - Date of First Recorded CR or PR)+1) *12/365.25

The primary analysis for DOR will be based on the investigator-assessed response. DOR will be summarized by each cohort and overall for expansion phase. The analyses will be performed for efficacy evaluable population.

Imaging - Related:

Pilot Phase:

- **To estimate the correlations between FMX-MRI, TAM levels, and tumor levels of irinotecan and SN-38 with administration of MM-398**
Scatter plot of FMX-MRI vs. tumor SN-38 level, TAM level and irinotecan level will be presented. For FMX-MRI, corrected FMX results across all scanned lesions at the same timepoint for a patient will be used. If there is more than one image data at the same timepoint for a patient, image data will be averaged first before summarizing.
- **To determine the value of FMX-MRI in directing tissue biopsy**
The value of FMX-MRI in directing tissue biopsy will be evaluated by summarizing the feasibility of ferumoxytol (FMX) quantitation in tumor lesions, feasibility of FMX-MRI to identify tumor associated macrophages (TAM), and the relationship assessment between ferumoxytol (FMX) tumor uptake and tumor response.

Expansion Phase

- **To assess the association between deposition, as visualized by ferumoxytol imaging, and measures of efficacy**
The association will be performed on per lesion basis. The analysis will be combined into primary endpoint analysis "The Relationship Between Ferumoxytol (FMX) tumor uptake and tumor response to MM-398" in section 11.1
- **To assess the analytical performance of FMX-MRI measurements and optimize FMX-MRI parameterization**

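### SAP 11.2 names Fisher's exact test for a primary Expansion objective but sets no response categories, leaves 'best' change undefined, and discards most of the information by cutting both variables

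*SAP*

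**What the plan says.** SAP 11.2, Expansion Phase, takes corrected FMX from target lesions at the 24-hour scan. When a patient has several lesions it averages them: "For patient with multiple target lesions, average corrected FMX results should be used for analysis". It then splits patients into low and high uptake at the overall median. For the outcome it says "Change in tumor size is used to assess tumor response to MM-398", and "For patient with multiple target lesions, the best change in tumor size achieved should be used". The analysis is: "The relationship between dichotomous FMX tumor uptake classification and tumor response to MM-398 will be assessed using Fisher's exact test".

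Three other places bear on the same relationship:

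- Protocol 10.6 ties the test to objective response: "informal Fisher's exact test will be used to investigate dichotomous FMX cutpoints as related to ORR". It also says "The relationship between FMX uptake at 1-4 hours and/or 24 hours with tumor response will be evaluated using various parameters and methods".
- SAP 11.3.1 sets up a central reading with algorithmic response classes: "The radiological tumor response will be reported separately for associating with ferumoxytol (FMX) uptake".
- SAP 11.3.2.5 (imaging-related, Expansion Phase), on deposition and efficacy, says "The association will be performed on per lesion basis" and folds that analysis into the primary one.

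**The concern.** Fisher's exact test needs a categorical outcome. SAP 11.2 supplies a continuous one and no cut, so whoever programs the table must choose the categories.

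The lesion rule is also open. If 'best' means the best lesion, the outcome comes from one lesion while the exposure is an average over all of them, and patients with more target lesions have more chances of a favourable value. If it means the best visit, the two sides can match. The text allows either.

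Protocol 10.6 (ORR) and SAP 11.3.1 (central classification) could each supply categories, but SAP 11.2 names size change and refers to neither. Two competent teams could therefore report different tables from the same data for a primary objective. Even once a cut is chosen, a 2x2 table is an imprecise summary in about 30 patients.

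**Working it through.** **The plan's own figures.** SAP 4 gives two binomial tails at a true ORR of 30% with n = 30. Recomputed: P(at least 14) = 0.0401 (stated 0.04) and P(at least 13) = 0.0845 (stated 0.084). Both reproduce. The documents give no figure for the FMX analysis itself.

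**Inputs.** From the documents: about 30 Expansion patients (SAP 4); median split of uptake (SAP 11.2), so 15 v 15 with 30 evaluable; ORR around 29% with 95% CI 14.6 to 46.3%, and other studies at 5 to 32% (SAP 4). Assumed: bivariate normality, and lesion or patient correlations where shown. The two-sided 0.05 level is only a yardstick, since the plan sets no alpha.

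**1. Best lesion favours patients with more lesions.** Suppose lesion changes are independent with mean 0 and SD 20% (assumed). One lesion shrinks by at least 30% with probability Φ(−1.5) = 0.067. For k lesions the best one does so with probability 1 − 0.933^k: 13% for k = 2 and 29% for k = 5. Correlated lesions would lessen this.

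**2. Information kept after both cuts.** Near zero correlation, each cut keeps φ(z)²/[p(1−p)] of the information, relative to Pearson.
- Median cut of uptake: 0.159/0.25 = 2/π = 0.637.
- Response cut at p = 0.30: φ(z) = 0.348, so 0.121/0.21 = 0.576.
- Product: 0.637 × 0.576 = 0.366, or about 37%. At p = 0.146 it is 0.268; at p = 0.05 it is 0.143.

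**3. What the 2x2 can show if response means CR/PR.** Exact Fisher p and conditional 95% limits for the odds ratio:

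| Split | Responders, high v low | p | OR (95% CI) |
|---|---|---|---|
| 15 v 15 | 4 v 0 | 0.100 | lower limit 0.73 |
| 15 v 15 | 5 v 0 | 0.042 | lower limit 1.07 |
| 15 v 15 | 6 v 3 | 0.43 | 2.6 (0.41 to 20) |
| 15 v 15 | 7 v 2 | 0.11 | 5.4 (0.76 to 65) |
| 15 v 15 | 8 v 1 | 0.014 | 14.5 (1.5 to 759) |
| 10 v 10 | 4 v 0 | 0.087 | lower limit 0.77 |

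So with four or fewer responders, even perfect separation leaves an interval that includes 1. The binomial chance of four or fewer is 0.549 of 30 at a true 14.6% and 0.039 at 29%. With 20 evaluable patients it is 0.843 and 0.269.

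**4. Detection rates, with test size disclosed.** With 9 of 30 responders, p < 0.05 needs 8 v 1 or more extreme in either direction. Under no association that has probability 0.014, so Fisher's actual size is 1.4%, not 5%. Simulation at n = 30, one value per patient:

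| Assumed correlation | Fisher | Spearman at 5% | Spearman at Fisher's size |
|---|---|---|---|
| 0.3 | 7% | 33% | about 17% |
| 0.5 | 21–22% | 77% | about 60% |

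The last column is the fair comparison for lost information.

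**5. Precision of the alternative.** Fisher z with SE = √[(1 + r²/2)/(n − 3)]. For an observed r of 0.45, z = 0.485. At n = 30, SE = 0.202 and the interval is 0.09 to 0.71. At n = 20, SE = 0.255 and the interval is −0.01 to 0.75.

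**The case against.** The strongest reply is that a coherent reading exists. SAP 11.2 tests tumor response, SAP 11.3.1 classifies it centrally for this purpose, and Protocol 10.6 names ORR, so one cross-reference would largely close the category gap. That is fair as far as it goes. But SAP 11.2 names size change as the measure, SAP 11.1 also speaks of change in lesion size, and the cross-reference is not there. The meaning of 'best' and the unit of analysis would remain open.

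Several stronger readings are tempting and are not supported:

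- **The time point is open.** SAP 11.2 fixes 24 hours, and Protocol 10.3 lets the SAP modify the protocol's analysis.
- **The reader is open.** SAP 11.3.1 already designates the central reading for the FMX association.
- **The population is in conflict.** SAP 11.1 opens by naming both the efficacy evaluable and PD evaluable sets, but that is a general lead-in; SAP 6 specifically assigns imaging-related efficacy to the PD evaluable set.
- **A test is planned where testing is banned.** SAP 7.4 says there will be none, but SAP 4 and Protocol 10.3 exclude only formal testing and Protocol 10.6 calls this test informal. This is wording.
- **Nothing continuous is planned.** Protocol 10.6 has continuous FMX summaries and a waterfall plot, and Protocol 10.9 has exploratory work on markers and efficacy. None of these specifies an estimate with an interval for this objective.

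It is also fair that preferring a correlation in an unpowered study is partly a choice of method, and that much of the raw gap in detection rates is Fisher's conservatism. The matched-size column above allows for the latter.

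**Conclusion.** The point holds as one of definition and precision, and should be settled before database lock. As written, the analysis of a primary objective cannot be run without inventing response categories, choosing a meaning for 'best', and deciding between patient and lesion as the unit.

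The 37% information figure rests on bivariate normality, a weak association and 30% responders. The result for four or fewer responders is exact but assumes a CR/PR cut, which SAP 11.2 does not set; a median cut would give about 15 responders. The 55% figure uses 14.6%, a lower confidence bound rather than a reported rate; at the plan's central 29% the chance is 4%. The correlations are assumptions, since the documents give none.

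A reader might infer an inflated false-positive risk from the open choices. The plan does not support that: there is no formal hypothesis, alpha, power target or decision tied to this test, and Fisher's test is conservative here. In simulated data with no association, trying four different response cuts gave any p < 0.05 in only 4.7% of trials.

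**What to change.** Amend SAP 11.2 as follows.

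1. **Main estimate,** in the PD evaluable population of SAP 6: Spearman correlation with a 95% bootstrap interval over patients. Correlate mean corrected 24-hour FMX over a patient's target lesions, as SAP 11.2 already sets, with the best-over-time percent change from baseline in the sum of diameters of those same lesions. Use the central reading of SAP 11.3.1.
2. **Lesion sites:** pool extracranial lesions from Cohorts 1 to 3, report Cohort 3 CNS lesions separately (Protocol 7.1.6 evaluates the two disease types separately), and state the resulting n for each.
3. **Per-lesion association** of SAP 11.3.2.5: a linear mixed model of lesion percent change on continuous corrected FMX with a random patient intercept, labelled as distinct from the patient-level estimate.
4. **Fisher table:** keep the median split against CR/PR as descriptive.
5. **SAP 7.4:** say that no formal testing will be done.

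The cost is SAP wording and slightly more analysis; no new data are needed. Protocol 10.3 requires an amendment if the change counts as a major modification of the primary endpoint or its analysis. A correlation is less simple to show than a 2x2 table, its interval stays wide, and the separate CNS estimate rests on about 10 patients at most.
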